31. Use of potent organic anion transporting polypeptide (OATP) inhibitors (e.g., IV rifampin, cyclosporine) within 5 half-lives of the drug prior to enrollment, if known.
32. Use of novel oral anticoagulants [NOAC] (including direct thrombin inhibitors such as dabigatran, or Factor Xa inhibitors such as rivaroxaban or apixaban), in preceding 3 days prior to the injury, if known.

Note: Patients in whom NOAC anticoagulation can be adequately reversed with Andexanet alfa may be enrolled after the Andexanet alfa infusion has been completed. This applies to the NOACs apixaban or rivaroxaban.

33. Use of antiplatelet therapy other than acetylsalicylic acid in the preceding 7 days prior to the injury, if known.
34. Use of vitamin K antagonists within 5 days prior to the injury, if known.

CONFIDENTIAL

The information contained herein may not be used, disclosed, or published without the written consent of Biogen MA Inc.

Note: patients on vitamin K antagonists who are subtherapeutic with INR < 1.5 may be included. If a patient can be adequately reversed from vitamin K antagonism to a subtherapeutic INR in time for randomization, this is acceptable, and the patient should be screened for enrollment.

Other

35. Females who are pregnant or women of childbearing potential with a positive urine or serum pregnancy test at the time of admission.
36. Nursing women who are unable to stop breastfeeding during study treatment infusion and for 7 days following the end of study treatment infusion.
37. Known current participation or known history of participation in any other investigational study that involved treatment with an investigational drug or device within 30 days prior to enrollment and for the duration of the current study participation.
38. Inability to comply with study requirements.
39. Other unspecified reasons that, in the opinion of the Investigator, make the participant unsuitable for enrollment.

CONFIDENTIAL

The information contained herein may not be used, disclosed, or published without the written consent of
Biogen MA Inc.

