11.2. Modification of Dose and/or Treatment Schedule

The dosage should not be modified unless due to hypoglycemia (sustained BG < 55 mg/dL [~ 3.1 mmol/L]). In the event of hypoglycemia, the study treatment infusion rate must be reduced as presented in [Table 4](#).

Table 4: Dose Modification Schedule

If hypoglycemia occurs within the first 6 hours of infusion:	
For participants on high infusion rate (0.2722 mg/h)	The infusion rate must be reduced to 0.1644 mg/h. If hypoglycemia cannot be rectified or reoccurs, the infusion rate must be further reduced to 0.0795 mg/h and must not be uptitrated.
For participants on low infusion rate (0.1644 mg/h)	The infusion rate must be reduced to 0.0795 mg/h and must not be uptitrated.
If hypoglycemia occurs after the first 6 hours of infusion:	
For all study participants	The infusion rate must be reduced to 0.0795 mg/h. The infusion rate can be uptitrated to 0.1134 mg/h when blood glucose is > 80 mg/dL (~ 4.4 mmol/L) for 3 consecutive readings.

If, at the reduced rate (0.0795 mg/h), hypoglycemia cannot be rectified by the treating team and the severity and length of hypoglycemia is determined by the Investigator to be harmful to the participant, treatment should be discontinued (see [Table 5](#) for further details).

If the study treatment needs to be temporarily stopped due to SOC ICU activities (e.g., transport of patient, IV-line changes or interstitial extravasation, etc.), the study treatment should be restarted as soon as possible per instructions in the DHA.

The infusion period will not be extended to account for any stoppages or reduction.

For mitigation strategies for hypoglycemia associated with dosing, please see [Table 5](#).

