11.4.1.1. Allowed Concomitant Therapy

11.4.1.1.1. Interventions Related to Blood Glucose

In a joint statement from the American Diabetes Association and the European Association for the Study of Diabetes, the International Hypoglycemia Study Group concluded that a BG level of < 54 mg/dL (~ 3.0 mmol/L) alone, without symptoms, is clinically important and should be included in reports of clinical studies involving glucose-lowering drugs [International Hypoglycaemia Study Group 2017]. The statement further recommends an “alert” level of 70 mg/dL (~ 3.9 mmol/L) for BG. The following interventions are designed in accordance with those recommendations; however, Investigators must use their own medical judgment in conjunction with referencing the guidance (Table 5).

Insulin

Insulin and other BG-lowering agents are not permitted during study treatment administration when BG < 140 mg/dL (~ 7.8 mmol/L).

Nutrition

Enteral nutrition is encouraged to be initiated within 24 hours of admission if consistent with SOC. Participants may need postpyloric administration of nutritional support.

Maintenance Dextrose-Containing IV Solution

During the study treatment infusion period, BG monitoring is required as follows:

- Hour 0 to Hour 24, monitor hourly (± 30 minutes)
- Hour 25 to Hour 48, monitor every 2 hours (± 30 minutes)
- Hour 49 to Hour 96, monitor every 4 hours (± 60 minutes)

See Section 5 for further details on timings of BG measurements. If treatment for hypoglycemia is initiated (for BG < 70 mg/dL [~ 3.9 mmol/L]), then BG monitoring is required every 15 minutes (± 10 minutes) until BG is ≥ 80 mg/dL (~ 4.4 mmol/L) for 3 consecutive readings without exogenous bolus glucose supplementation. BG monitoring may be performed more often at the discretion of the Investigator. Table 5 shows how BG should be monitored and managed according to inpatient BG levels.

Total fluid volume, inclusive of study treatment volume, infusion rate, infusion duration, sodium content, and percent of dextrose, should be guided by the clinical status of the subject and medical judgment.

CONFIDENTIAL

The information contained herein may not be used, disclosed, or published without the written consent of Biogen MA Inc.

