11.4.1.1.2. CYP2C9/CYP3A4 and Bosentan

BIIB093 is metabolized by cytochrome P450 (CYP) 2C9 and CYP3A4. Medications that are strong inhibitors or inducers of the CYP enzymes may elicit significant PK-mediated drug interactions with BIIB093 (see [Appendix 1](#)). Oral glibenclamide products do not contraindicate nor require dosage adjustment for concomitant use of inhibitors or inducer of CYP2C9 and CYP3A4. Therefore, for participants who require these medications during BIIB093 treatment, the use of these agents will be permitted in the study with additional monitoring per the Investigator's judgment (e.g., BG levels) to ensure participant safety.

Participants receiving treatment with bosentan during Screening can be included in the study, and liver function tests should be collected more frequently, if necessary, at the discretion of the Investigator.

CONFIDENTIAL

The information contained herein may not be used, disclosed, or published without the written consent of Biogen MA Inc.

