11.4.1.2. Disallowed Concomitant Therapy

Insulin and other BG-lowering agents are not permitted during study treatment administration when BG < 140 mg/dL (~7.8 mmol/L).

No other sulfonylurea agents may be administered during the hospital stay.

No other investigational drugs may be administered during the 180-day follow-up period.

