APPENDIX 1. MEDICATIONS THAT MODULATE CYP2C9 AND CYP3A4**CYP2C9**

Substrates	Inhibitors	Inducers
celecoxib	Moderate	Moderate
Glimepiride	amiodarone	rifampin
phenytoin	felbamate	enzalutamide
tolbutamide	fluconazole	aprepitant
warfarin	miconazole	carbamazepine
	piperine	ritonavir
	Weak	
	diosmin	
	disulfiram	
	fluvastatin	
	fluvoxamine	
	voriconazole	

Source: FDA 9/26/2016 Drug Development and Drug Interactions: Table of Substrates, Inhibitors, and Inducers.

CYP3A4

Substrates	Inhibitors	Inducers
midazolam	Strong	Strong
tacrolimus	ritonavir	phenytoin
sirolimus	indinavir	carbamazepine
naloxegol	nefazodone	rifampin
nisoldipine	saquinavir	
saquinavir	clarithromycin	
simvastatin	troleandomycin	
tipranavir	voriconazole	
triazolam	ketoconazole	
vardenafil	itraconazole	
budesonide	nefazodone	
dasatinib	grapefruit juice (bergamottin)	
alfentanil	boceprevir	
avanafil	cobicistat	

CONFIDENTIAL

The information contained herein may not be used, disclosed, or published without the written consent of
Biogen MA Inc.

buspirone	conivaptan	
conivaptan	danoprevir	
darifenacin	elvitegravir	
darunavir	lopinavir	
ebastine	paritaprevir	
everolimus	posaconazole	
ibrutinib	telaprevir	
lomitapide	tipranavir	
lovastatin	Moderate	Moderate
dronedarone	verapamil	bosentan
eletriptan	tofisopam	efavirenz
eplerenone	aprepitant	etravirine
felodipine	erythromycin	modafinil
indinavir	fluconazole	
lurasidone	cimetidine	
maraviroc	ciprofloxacin	
quetiapine	clotrimazole	
sildenafil	crizotinib	
ticagrelor	cyclosporine	
tolvaptan	dronedarone	
alprazolam	imatinib	
aprepitant	fluvoxamine	
atorvastatin	Weak	Weak
colchicine	ticagrelor	armodafinil
eliglustat	chlorzoxazone	rufinamide
pimozide	cilostazol	
rilpivirine	fosaprepitant	
rivaroxaban	istradefylline	
tadalafil	ivacaftor	
	lomitapide	
	ranitidine	
	ranolazine	
	tacrolimus	

Source: FDA 9/26/2016 Drug Development and Drug Interactions: Table of Substrates, Inhibitors, and Inducers.

CONFIDENTIAL

The information contained herein may not be used, disclosed, or published without the written consent of
Biogen MA Inc.

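### Potent OATP inhibitors are excluded at entry but not restricted during the 96-hour infusion, and the permission that reaches rifampin is argued on CYP enzymes alone: a minor safety inconsistency

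*Protocol*

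**What the plan says.** Entry. Criterion 31 in Protocol Section 8.2 excludes "Use of potent organic anion transporting polypeptide (OATP) inhibitors (e.g., IV rifampin, cyclosporine) within 5 half-lives of the drug prior to enrollment, if known". The lead-in to that section confines the criteria to study entry.

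On treatment. Section 11.4.1.2 disallows three things: insulin and other glucose-lowering agents when BG is below 140 mg/dL, other sulfonylureas ("No other sulfonylurea agents may be administered during the hospital stay"), and other investigational drugs. OATP inhibitors are not among them.

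Section 11.4.1.1.2 deals with metabolic interactions. It begins: "Medications that are strong inhibitors or inducers of the CYP enzymes may elicit significant PK-mediated drug interactions with BIIB093". It then gives its reason for not barring them: "Oral glibenclamide products do not contraindicate nor require dosage adjustment for concomitant use of inhibitors or inducer of CYP2C9 and CYP3A4". It concludes that "for participants who require these medications during BIIB093 treatment, the use of these agents will be permitted in the study with additional monitoring", with the monitoring left to the Investigator's judgment. The section points to Appendix 1, which lists rifampin and "cyclosporine", the two examples named in criterion 31.

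Section 11.2 adds that "The dosage should not be modified unless due to hypoglycemia". Section 11.4.1.1.1 allows that "BG monitoring may be performed more often at the discretion of the Investigator".

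**The concern.** A washout of 5 half-lives timed to enrollment makes sense only if the inhibitor should be absent when BIIB093 starts. Starting the same drug a few hours later, while the infusion runs, produces the co-exposure that the washout is meant to prevent. The protocol sets no rule against this. For rifampin a site that looks it up finds a permission, supported by an argument about a different interaction pathway.

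What is at stake is the coherence of the safety rules, with hypoglycemia as the principal known risk. Study drug may not be reduced in anticipation, so the levers left to the site are BG monitoring and dextrose, and no monitoring frequency is stated for this case.

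**Working it through.** There is no planned figure to reproduce. The check sets the texts side by side, then counts the burden of the fix.

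**1. Which entry exclusions have an on-treatment counterpart?**

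| Drug class | Entry rule (Section 8.2) | Rule in Section 11.4.1.2 |
|---|---|---|
| Sulfonylureas | Criteria 18 and 25 | Barred during the hospital stay |
| Investigational drugs | Criterion 37 | Barred to Day 180 |
| Potent OATP inhibitors | Criterion 31, timed to enrollment | None |
| NOACs, antiplatelets other than acetylsalicylic acid, vitamin K antagonists | Criteria 32 to 34, timed to the injury | None |

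Criterion 31 is therefore not the only medication criterion left out. It differs from 32 to 34 in being timed to enrollment.

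**2. Does another section fill the gap?** Sections 10.1, 11.2 and 11.3 do not mention OATP inhibitors. The bar on unapproved therapies in Section 11.4.2 sits under concomitant procedures and does not name them. Apart from criterion 31 and the abbreviation lists, OATP appears only in Section 13.4, which names OATP1B1 among genes that might affect safety and efficacy.

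**3. How far does the CYP permission reach?** Appendix 1 lists rifampin as a moderate CYP2C9 inducer and a strong CYP3A4 inducer, and cyclosporine as a moderate CYP3A4 inhibitor.

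- Narrow reading: the permission covers the strong agents with which Section 11.4.1.1.2 opens. Rifampin is permitted and cyclosporine is not addressed.
- Broad reading: it covers all of Appendix 1, because the stated reason refers to inhibitors and inducers without a strength. Both drugs are permitted.

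On either reading, nothing restricts starting cyclosporine.

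**4. Can the risk be sized?** Section 4.5.1.2 gives a simulated steady-state mean of 40 ng/mL at 5 mg/day (95% CI 13.4 to 61.8) and a severe-hypoglycemia threshold of 75 ng/mL. The headroom is 75/40 = 1.88-fold from the mean and 75/61.8 = 1.21-fold from the upper limit. Whether an OATP inhibitor would use any of it cannot be computed: the documents give no effect size, direction or frequency of use. Appendix 1 lists rifampin only as an inducer, and Section 4.5.1.2 reports no apparent relationship between concentration and BG.

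**5. Burden of closer monitoring.** Routine checks under Section 11.4.1.1.1:

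- Hours 0 to 24, hourly: 25
- Hours 26 to 48, every 2 hours: 12
- Hours 52 to 96, every 4 hours: 12
- Total: 25 + 12 + 12 = 49

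Extra checks if monitoring becomes hourly for the rest of the infusion:

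| Inhibitor started | Hourly checks to Hour 96 | Routine checks | Extra |
|---|---|---|---|
| Hour 24 | 72 | 12 + 12 = 24 | 48 |
| Hour 48 | 48 | 12 | 36 |
| Hour 72 | 24 | 6 | 18 |

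A start before Hour 24 also adds 48, because the routine is already hourly until then. These counts follow the protocol schedule. SAP Section 5.7.4 describes point-of-care glucose as collected hourly to Hour 96. If that is the actual practice, the extra is zero.

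**The case against.** The strongest reply is that entry rules may properly be stricter than on-treatment rules. The medication criteria concern drugs taken before randomization, none of criteria 31 to 34 is carried forward, and Section 7.3 leaves acute care to the attending clinician. Section 10.1 takes a similar line: a sulfonylurea exposure that comes to light during treatment is not a cause for stopping. This shows that the gap may be deliberate. But sulfonylureas and investigational drugs are carried forward, and the reason given for the CYP permission does not explain why an OATP inhibitor is acceptable once dosing has begun.

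The second reply is that the safeguards already cover the hazard. Checks are scheduled throughout. Dextrose is recommended below 120 mg/dL and titrated toward 140 to below 180 mg/dL, a bolus is mandatory below 70 mg/dL, a rate cut is mandatory below 55 mg/dL, and discontinuation rules follow. These operate whatever the cause of a low reading. This stands, and it is the main reason the point is minor.

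The third reply is that no document supports hourly checks over another interval. That also stands; hourly is only an example.

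A reader might infer more: that participants face a demonstrated excess risk of hypoglycemia, or that the treatment comparison is affected. The documents support neither, since they give no OATP effect on exposure and no rate of use. Nor is it right that the protocol is silent on both drugs, because rifampin falls within the permission and its additional monitoring.

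**Conclusion.** The inconsistency holds on the text and should be corrected, as a minor safety point. The protocol leaves open during the infusion a co-exposure that it excludes at entry, expressly permits rifampin, and justifies that permission on CYP grounds only.

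Confidence is high on what the sections say. It does not extend to clinical consequence, whose size and direction cannot be derived from the documents. Nothing here bears on sample size, power or Type I error. The conclusion is limited to the protocol and SAP: the Investigator's Brochure, the Study Reference Guide and the Directions for Handling and Administration were not available and may contain guidance for sites.

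**What to change.** Add to Section 11.4.1.2: *Potent OATP inhibitors, such as IV rifampin or cyclosporine, should not be started during study treatment infusion unless clinically necessary with no suitable alternative.*

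State in Section 11.4.1.1.2, and in a footnote to rifampin and cyclosporine in Appendix 1, that the CYP permission alone does not cover these drugs.

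If one is needed, continue study treatment with closer BG monitoring than the routine schedule, for example hourly to the end of the infusion. Discontinuation should not be the default; it stays with the Investigator under Section 10.1. Stopping has a data cost: SAP Section 3.4 treats images as on-protocol only before early termination of the infusion, although SAP Appendix 1 omits that limit, so the Hour 96 read could be lost. Stopping within 12 hours also removes the participant from the per-protocol set (SAP Section 3.6.2).

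The cost is wording in two sections and one footnote, with no new visits or analyses. An affected participant would have the extra checks counted above and occasionally a narrower choice of drug. Because assignment is blinded, the rule must apply to placebo participants as well.

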9. SCREENING AND RANDOMIZATION

9.1. Screening

Participants, their LAR, or physician per local requirements must provide informed consent before any screening tests are performed (see Section 17.3). Determination of whether consent by a LAR is required (and if so, determination of the LAR) as well as specific details of the consenting process will be determined by country law, state law, and local ethics committee requirements. The study team is encouraged to use fax, telephone, and/or telemedicine consent if allowed by country law, state law, and local ethics committee rules. Participating study sites are required to document all screened candidates initially considered for inclusion in the study.

All participants arriving at the recruiting site with potential for dosing within the 10-hour window, and having a brain contusion due to a non-penetrating head injury should be considered for inclusion in this study.

A screen failure log will be maintained at each study site. Participants are eligible for rescreening (i.e., an additional study-specific imaging scan), provided they meet the protocol-specified time window and all inclusion/exclusion criteria. Screen failures are defined as participants who have been diagnosed with brain contusion, signed the informed consent form (ICF), but are not subsequently randomized. If a participant is considered a screen failure, the reasons for exclusion must be documented in the participant's source documents and on the screening log. A minimal set of screen failure information is required to ensure transparent reporting of screen failure participants to meet the Consolidated Standards of Reporting Trials publishing requirements and to respond to queries from regulatory authorities. Minimal information includes demography, screen failure details, eligibility criteria, and any SAE.

SAEs occurring during the screening period will be recorded on an SAE form; however, SAEs do not need to be recorded or followed once a participant is confirmed as a screen failure.

Because pertinent participant information will already be collected as part of SOC, and to reduce additional study-specific procedures, baseline information may be taken from the participant's medical records prior to obtaining informed consent. However, informed consent will be obtained prior to performing any study-specific procedures.

A short suicidal ideation/behavior questionnaire will be conducted on participants who are alert and capable of providing answers at Screening (prior to dosing). For these participants, this questionnaire should be repeated at Days 30, 90, 180, and ET Visit.

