¹⁰ The optional blood sample for pharmacogenetic analysis requires a separate informed consent form to be administered between the start of study and hospital discharge. The pharmacogenetic sample should be collected as close to the consenting procedure as possible and preferably within 24 hours of the start of study treatment. The date and time of collection should be recorded.

¹¹ A delayed intubation eCRF must be completed if a participant is intubated for deteriorating neurologic status.

¹² Hourly (\pm 30 minutes) for Hour 0 to Hour 24, every 2 hours (\pm 30 minutes) for Hour 25 to Hour 48, and every 4 hours (\pm 60 minutes) for Hour 49 to Hour 96. If treatment for low BG (< 70 mg/dL [\sim 3.9 mmol/L]) is initiated, then BG monitoring is required every 15 minutes (\pm 10 minutes) until BG is \geq 80 mg/dL (\sim 4.4 mmol/L) for 3 consecutive readings without exogenous bolus glucose supplementation. See Section 11.4.1.1.1 for details on BG monitoring and management.

¹³ [REDACTED] A CMO eCRF must be completed for participants for whom care is withdrawn.

¹⁴ An NCCT scan is sufficient for participants who cannot get an MRI.

¹⁵ The 96 hour scan should be performed after study treatment infusion is complete, within 18 hours of the Hour 96 time point.

¹⁶ Only required if ET occurs before the Hour 96 scan has been performed.

¹⁷ Includes all AEs from the beginning of study treatment administration and all SAEs from the time of consent. AEs of special interest (hypoglycemia [BG < 55 mg/dL (\sim 3.1 mmol/L)]) will be upgraded to an SAE. See Section 15.3 for further details on monitoring and recording AEs.

¹⁸ A short suicidal ideation/behavior questionnaire will be conducted on participants who are alert and capable of providing answers at Screening (prior to dosing). For these participants, this questionnaire should be repeated at Days 30, 90, 180, and ET Visit. The questionnaire conducted at Screening will record “Life Time” events and subsequent visits (at Days 30, 90, 180, and ET Visit) will record “Since the Last Visit” events.

CONFIDENTIAL

The information contained herein may not be used, disclosed, or published without the written consent of Biogen MA Inc.

Table 3: ECG, [REDACTED] Schedule of Activities

	12-lead ECG¹	
Predose	SOC ECG taken at Screening	
Minute 5	±5 minutes	
Hour 6	±5 minutes	
Hour 24	±5 minutes	
Hour 48	±5 minutes	
Hour 72	±5 minutes	
Hour 96	±5 minutes	

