8. SELECTION OF PARTICIPANTS

8.1. Inclusion Criteria

To be eligible to participate in this study, candidates must meet the following eligibility criteria at Screening, or at the timepoint specified in the individual eligibility criterion listed:

1. Ability to understand the purpose and risks of the study and provide signed and dated informed consent and authorization to use confidential health information in accordance with national and local subject privacy regulations *or* consent provided by an independent physician where local regulations allow, and/or provision of informed consent by the participant's legally authorized representative (LAR) in accordance with all local and national regulations *or* according to the local ethics committee's guidelines *or* by another process compliant with applicable national laws and regulations and ethics committee requirements.
2. Aged 18 to 85 years old, inclusive, at the time of informed consent.

Note: age 18 years at the time of informed consent or participant meets the minimum age of consent in accordance with national regulations (whichever is higher).

Note: for countries where the minimum age of consent is over 18 years, participants may be enrolled provided a LAR is available, and if capable, the participant assents to treatment. The LAR must consider the participant's involvement in the study and provide informed consent for the participant.

3. A score of 5 to 15 on the GCS. Assessment should be made prior to medical intervention, where possible.

Note: an enrollment cap on participants presenting with GCS 15 will be placed at 10% of total number of participants.

4. A clinical diagnosis of brain contusion with lesions within the supratentorial brain parenchyma totaling > 3 mL in volume on noncontrast computed tomography (NCCT) scan (allowing for multiple contusions) at Screening.

Notes:

- a. Participants with multifocal contusions totaling > 3 mL in volume will be included. The sum total of contusion volumes should be calculated based on the baseline imaging.
- b. Contusion volume for a single contusion (hyperintense hematoma and hypointense edema on NCCT) must be determined and documented by the Investigator or his/her designee using study-specific methods detailed in the Imaging Manual.
- c. If more than 1 NCCT scan is performed prior to randomization, eligibility should be based on the most recent NCCT scan.

CONFIDENTIAL

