14.1. Clinical Safety Assessments

The following clinical assessments will be performed to evaluate the safety profile of BIIB093:

- Medical history
- Physical examinations, including weight and height (may be estimated)
- Vital sign measurements: temperature, pulse rate, systolic and diastolic blood pressure, respiratory rate, and oxygen saturation
- 12-lead ECGs
- Concomitant therapy and procedure recording

All medications, including but not limited to dextrose solutions, osmotherapy, paralytics, sedatives, and vasoactive drugs used through Day 180 are to be recorded in the eCRF. Concomitant procedures will be recorded through Day 180.

- AE and SAE recording
- Assessment of suicidal ideation/behavior at Screening and follow-up in patients whose level of consciousness is compatible with completion of the abbreviated suicidal ideation/behavior questionnaire. Investigators should use their best judgment to identify patients suitable for this assessment.

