Rationale: This change was made to comply with regulatory draft guidance stipulating that prospective suicidal ideation and behavior assessments should be carried out in all clinical trials involving any drug being developed for CNS activity. This assessment will only be carried out in participants deemed capable of understanding and appreciating the content of the questionnaire. In addition, this change was made to understand any possible association between BIIB093 and suicidal ideation in participants with brain contusion.

This change also affects Section 5, Schedule of Activities (Table 2) and Section 14.1, Clinical Safety Assessments.

Section 9.3, Blinding Procedures

Change: The blinding procedure was clarified.

Now reads:

The study Sponsor and CRO study management team will be fully blinded for the study. ~~When~~~~After~~ the last participant completes their Day 904 visit, the clinical study database will be locked and designated personnel at the Sponsor will be unblinded for the purposes of evaluating the primary and secondary efficacy analyses. The final database lock will occur

CONFIDENTIAL

The information contained herein may not be used, disclosed, or published without the written consent of Biogen MA Inc.

whenafter the last participant completes their Day **90 Visit and the long-term follow-up database will be locked after the last participant completes the Day 180 Follow-up Visit.** The Sponsor and CRO study management teams responsible for all site interactions and data entry will remain blinded **through Day 180** to individual treatment assignments ~~during the study~~.

Rationale: This change was made to clarify that blinding will be maintained until the End of Study for data integrity of long-term functional outcomes.

Change: [REDACTED]

Now reads: [REDACTED]

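### The follow-up suicidality questionnaire is scheduled only for participants who could answer it at Screening, so those who regain capacity later are not scheduled for it

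*Protocol*

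**What the plan says.** Protocol section 9.1 and footnote 18 to the Schedule of Activities (Table 2) set the rule in two sentences. The first defines who is asked at entry: "A short suicidal ideation/behavior questionnaire will be conducted on participants who are alert and capable of providing answers at Screening (prior to dosing"). The second defines who is asked again: "For these participants, this questionnaire should be repeated at Days 30, 90, 180, and ET Visit". Footnote 18 adds that the Screening questionnaire records lifetime events and each later one records events since the previous visit. SAP Appendix 2 copies the footnote.

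Section 14.1 lists the same item among the clinical safety assessments in different terms: "Assessment of suicidal ideation/behavior at Screening and follow-up in patients whose level of consciousness is compatible with completion of the abbreviated suicidal ideation/behavior questionnaire". It continues: "Investigators should use their best judgment to identify patients suitable for this assessment". Section 14 opens by referring to Section 5 for the timing of all safety assessments.

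On who enters the trial, inclusion criterion 3 requires "A score of 5 to 15 on the GCS", and its note says that "an enrollment cap on participants presenting with GCS 15 will be placed at 10% of total number of participants". Criterion 1 allows consent by a legally authorized representative or, where permitted, an independent physician.

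**The concern.** The second sentence of the rule fixes the follow-up group by a state observed before dosing, within about 10 hours of a head injury. That state is often transient. Someone who is obtunded on arrival and conversing normally at the Day 30 visit is outside the group, although that visit takes place and already collects other outcomes and adverse events.

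The participants left out would tend to be those with more impaired consciousness at entry. The Version 2 amendment summary, cited here only for purpose, says that the assessment was added to follow regulatory draft guidance and to look for any link between BIIB093 and suicidal ideation in this population. The limit it states is present capability: "This assessment will only be carried out in participants deemed capable of understanding and appreciating the content of the questionnaire". A rule tied to Screening status is narrower than that. At stake is how completely suicidality is screened in a structured way among recovered participants, and to whom the results apply.

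**Working it through.** No figure in the plan needs reproducing, so the check is a comparison of texts.

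1. **Who are the participants referred to in the repeat instruction?** In section 9.1 and in both copies of footnote 18, the only preceding group is the one able to answer at Screening before dosing.

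2. **Does any other text start the questionnaire later?** None found. The Table 2 row marks Screening, Days 30, 90 and 180, and early termination, but footnote 18 governs that row.

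3. **Worked case:** a participant enters at GCS 7, cannot answer at Screening, and is awake and oriented at Day 30.

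| Source | Questionnaire at Day 30? |
|---|---|
| Protocol 9.1 | Not scheduled |
| Protocol Table 2, footnote 18 | Not scheduled |
| SAP Appendix 2, footnote 18 | Not scheduled |
| Protocol 14.1, consciousness judged at each assessment | Yes |
| Protocol 14.1, read as the section 9.1 group | Not scheduled |

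4. **Recall period.** A site that follows the first reading of 14.1 has no defined recall window. Lifetime recall is assigned to Screening only, and since-last-visit recall presupposes an earlier questionnaire.

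5. **Is the case foreseeable?** Yes. GCS 5 to 8 and 9 to 12 are randomization strata (section 9.2), surrogate consent is provided for, and section 11.4.2.2 anticipates intubation in the emergency room or trauma bay.

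6. **How many?** The documents give no GCS distribution and no count of participants unable to answer. The cap allows 0.10 × 160 = 16 participants at GCS 15, which leaves at least 160 − 16 = 144 at GCS 5 to 14 if 160 enrol and the cap is respected. This is not an estimate of the number left out: a score below 15 does not by itself mean inability to answer, and some who cannot answer at entry will die or stay too impaired at every visit.

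**The case against.** The best defence is that the restriction is deliberate and coherent. A lifetime record before dosing followed by since-last-visit records gives each participant a baseline. Because membership is settled before treatment starts, comparing arms within that group is protected by randomisation. Adding people because they are able to answer at Day 30 or later selects on survival and recovery, which the trial hopes the drug will improve. This stands. It is a reason to keep the Screening-assessed group as the comparison and to report the added group apart from it, but not a reason to leave the added group unscreened.

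A reader might infer that section 9.1 contradicts section 14.1. The documents do not go that far. Section 14 hands timing to Section 5, whose footnote agrees with 9.1, and 14.1 neither says at each visit nor mentions later recovery. The two are in tension and need reconciling.

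A reader might also infer that the omitted participants are never assessed for suicidality. That is too strong. Sections 15.3.1 and 15.3.3 require adverse events to be sought at each study visit and serious events to be recorded from consent to last follow-up, for everyone. What is missing is the scheduled, structured questionnaire.

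Finally, drug relevance at follow-up is limited. The infusion lasts 96 hours and the SAP's on-treatment period ends 72 hours later: 96 + 72 = 168 hours, or 7 days. The earliest in-window Day 30 visit is 30 − 7 = Day 23. Apart from early termination visits, every repeat therefore falls well after exposure. This lowers the stakes, but it applies equally to the participants already scheduled.

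**Conclusion.** The point holds as a gap in coverage. As written, a participant who cannot answer at Screening and recovers by Day 30, 90 or 180 is not scheduled for the questionnaire, and section 14.1 leaves room for sites to act differently. This rests on the plain reading of the repeat instruction and on the assumption that some participants who cannot answer at entry become able to later, which the eligible GCS range makes likely.

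Its size cannot be stated. No percentage unable to answer, and no precision figure built on one, has support in the documents. Nor do they show that only the mildest injuries are covered, since participants with GCS 13 or 14, and some with lower scores, may be able to answer.

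Screening status precedes dosing, so the restriction does not in itself bias one arm against another. The primary endpoint, power and type I error are unaffected. The change is worth making because it is inexpensive and concerns safety data, but the trial's main conclusions do not depend on it.

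**What to change.** Amend section 9.1 and footnote 18, with the SAP Appendix 2 copy, so that at Days 30, 90, 180 and early termination the questionnaire goes to every participant who is alert and capable at that visit, whether or not one was completed at Screening. For a first questionnaire after Screening, define the recall period: lifetime events before the injury, and events since the start of study treatment, recorded separately. Align section 14.1 so that all the texts state the same rule.

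In the SAP, tabulate results by actual treatment group, split by whether a Screening questionnaire exists. Keep the Screening-assessed group as the baseline-defined comparison and label the later-assessed group as descriptive. The unredacted part of SAP section 5.7 shows no suicidality summary; redacted text may contain one, in which case only the split needs adding.

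The cost is a short protocol clarification and a few minutes at visits already scheduled. Two limits remain: late first questionnaires have no pre-dose value, and the added group is selected on survival and recovery after randomisation. The split isolates that selection but does not remove it.
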